**Urinary Incontinence Self-Screening For Healthy Aging**  
**Study Protocol and Statistical Analysis Plan**  
**April 4, 2018**

## Urinary Incontinence Self-Screening For Healthy Aging

### o Background

Urinary incontinence (UI) is the involuntary loss of urine that affects 3.5 million Canadians, or nearly 10% of the population. According to the Canadian Urinary Bladder Survey, 16% of men and 33% of women over the age of 40 have symptoms of urinary incontinence. Urinary incontinence prevalence rates have been reported between 9 and 59% in those aged 50 and above. The prevalence of incontinence increases with age with the Canadian Urinary Bladder Survey reporting an increase in urinary symptoms in those 65 years and older.

The impact of UI on older adults can be significant with serious physical, psychological, and social consequences. UI is associated with serious medical consequences such as falls, fractures, institutionalization, and death. Embarrassment, isolation, depression, decreased self-confidence, disruption in normal activities and lowered quality of life are pervasive. On average, older adults with UI suffer in silence for four years before they seek health care, instead making adjustments in their daily lives to manage the incontinence.

As many as 50% (or more) of older adults with UI have never discussed or sought help from their general practitioner (GP), often due to erroneous beliefs about incontinence, such as the condition being age-related and untreatable. However, older adults with UI seeking help from their GPs have reported negative experiences of being brushed aside, treated with indifference, and not having their UI-related symptoms recognized or prioritized. Preference for self-referral over physician referral emerged in a recent study with a five year (2010-2015) increase of 480% in self-referral to urogynecology, the highest increase in all types of referrals (e.g., specialist, GP).

The importance of early detection and referral is critical. Left undetected and untreated, urinary incontinence is a progressive problem that worsens over time creating greater management challenges for both patients and health providers. Identification of patients with early or less troublesome urinary symptoms may aid in early intervention with simple measures (e.g., lifestyle advice, behavioural therapy), and reduce the need for more complex and costly treatment. Although older adults with UI are receptive to being asked about incontinence, UI screening has yet to become standard practice. As health care has increasingly become patient-centered and shifted responsibility to patients, self-screening has greater potential to reach older adults and promote earlier identification, referral and intervention.

Self-screening has been shown to have several benefits including enhanced privacy in sensitive situations, increased self-awareness, and reaching a wide audience. It has

been used with a variety of populations and health conditions (e.g., cancer)  and social challenges (e.g., driving)  and is well suited to the study of incontinence because of the stigma, embarrassment and silence that surrounds this health condition. Opportunities for IU self-screening may provide older adults with validation, acceptance, support of a problem shrouded in silence and facilitate help seeking.

**o Objectives:** The overall aim is to increase awareness of urinary incontinence in community-based older adults and promote timely treatment. To achieve this aim the project objectives will include:

1. To develop a self-screening process for community-based older adults
2. To test the use of a self-screening process with community-based older adults

## **o Methods**

**Study Design:** This study will use a pilot randomized control trial to test the effectiveness of a self-screening process with older adults. The hypothesis is that older adults exposed to the self-screening process will follow up with health professionals to receive help for the UI condition. There will be two groups of older adults. The intervention group will participate in self-screening and the control will not be exposed to self-screening. Using this approach is necessary to determine whether or not the self-screening works.

*Intervention:* The intervention will include a combination of self-screening and UI specific information and resources. Older adults in the intervention group will complete a gender specific UI Self-Screening tool. Men will complete the International Consultation on Incontinence Modular Questionnaire (ICIQ) for Males  (**See ICIQ-M**) and women will complete the ICIQ for Females. (**See ICIQ-F**). The ICIQ Male and Female are valid and reliable tools, recognized by the International Continence Society, and collect more information about urinary symptoms than other tools, an advantage for referral purposes. In addition, the intervention group will receive a fact sheet with UI specific information, contact information to the local incontinence clinic and a link to a website with patient incontinence resources and education (**See UI Fact Sheet**).

*Control Group:* Older adults assigned to the control group will receive standard care from their physicians. Standard care may differ from general practitioner to general practitioner. Usual care for urinary incontinence (UI) from general practitioners is generally minimal. Most patients do not tell their physicians about UI, and most physicians do not ask about UI. If this topic does come up during a GP appointment, a patient may be offered no treatment, lifestyle advice (e.g., do not drink before bed), told to do Kegels (but likely not instructed how to do these properly) or in some cases, offered pharmacological therapies (which will be captured in our questionnaire with the participants). But standard of care is unfortunately very often no care.

**Setting:** Senior's Centers and organizations dedicated to seniors in Kelowna, West Kelowna and Lake Country will serve as the recruitment sites for this study. These Senior's Centers/organizations (e.g., Lake Country Seniors Centre, Lake Country

Health Planning Society, Westside Health Network, Seniors Outreach Bureau) serve large and different populations of seniors (>300 seniors) so overlap in membership is not expected to be an issue.

**Sampling and Recruitment:** The study sample will include older adults  $\geq 65$  years of age (men and women) who attend a local Senior's Centre or organization, report having some UI symptoms, are independent living, ambulatory, with no more than mild cognitive impairment, able to read and write in English or have someone who can assist with reading the data collection information and can complete a paper survey independently. Older adults will be excluded if they have cognitive impairment, require more than minimal assistance with completing the survey, or have any impairment (e.g., vision) that would make self-screening and follow up challenging. They must also never have been referred to a UI specialist or program in the past.

Following ethics approval, eligible older adults will be recruited through a letter of invitation sent through e-mail distribution lists of our participating seniors centres/organizations (**see Letter of Invitation**). Based on other UI studies, in which there was a 14% self-referral rate without an intervention, we hypothesize a 61% incremental increase in self-referral in the arm receiving the intervention. The sample size required to detect an improvement in self-referral (with 80% power,  $p < .05$ ) to a health professional (e.g., UI specialist) is 24 participants (12 older adults per arm). Drop-out or attrition is common in research studies. In factoring the potential for a drop-out rate of 50%, a sample size of 36 participants will be recruited. Excel randomization function will be used to assign participants to one of the two arms (the arm receiving the self-screening process or the arm not receiving this process). The randomization assignments (allocations) will be placed in individual sealed envelopes. After informed consent is obtained, the Research Assistant (RA) will choose the next available envelope to reveal which arm the study participant will be assigned.

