### **Data Collection:**

*Pre-test:* Prior to implementation, the self-screening tool will be pre-tested with 5 older adults attending participating seniors centres/organizations. The purpose of the pretest will be to identify any implementation issues such as recruitment, administration, understanding and ease of use of the self-screening tools.

*Procedures:* Older adults assigned to both groups will receive follow up from the RA who will provide details about the study and answer any questions. Prior to randomization, consenting older adults from both groups will complete a demographic (e.g., age, sex, highest level of education, household income), health history profile (e.g., co-morbidities, history of previous referrals for UI, medications) (**see Demographic and Health History Profile**) and a quality of life questionnaire (**see The King's Health Questionnaire**).

Three months following study entry participants from both groups will receive a phone follow-up to obtain information about actions they have taken re IU (e.g., self/physician

referral), UI symptoms,  treatments received, satisfaction with care (**See Three Month Follow up Questionnaire**), and changes in quality of life. The follow up phone call will be recorded. It is expected the baseline and 3 month follow up data collection will take approximately 20-30 minutes to complete.

The primary outcome will be the numbers of older adults who take action to receive help for their UI during the 3-month follow-up from study entry: self-referral to the local UI clinic, appointment with GP about their UI, and/or referral to a specialist (urologist or urogynecologist or gynecologist), or other action. Secondary outcomes will include: treatments received, satisfaction with care, changes in quality of life.

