**Post-Intervention Focus Groups:** To obtain feedback on the self-screening process, focus groups (n=2) will be conducted with older adults (10-12 participants) who were in the self-screening group. At the end of 3-months from study entry, in conjunction with survey completion, participants will be invited to participate in a focus group. Those expressing an interest in focus group participation will be contacted with details of the date, time of the focus group and will receive a copy of the semi-structured interview questions. Questions will address participants' comfort with the self-screening process, rationale and influences on choice to self-refer or not, barriers/facilitators to self-referral, recommendations to make the self-screening process easier (**See Focus Group Interview Questions**).

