#### *Primary analysis:*

The study hypothesis is that older adults exposed to the self-screening process will follow-up with health professionals to receive help for their UI condition more often than the control group. To test this hypothesis, investigators will calculate the proportion (with 95% CI) of participants who self-report as having self-referred to a health professional (binary yes/no response) during the study period for each group. A chi-square test will be conducted to determine if the self-screening process is associated with self-referral to a health professional. In addition, a logistic regression analysis will be conducted to model the odds of self-referring among people who have undergone self-screening, adjusting for demographics, and health history variables. Bivariate analysis will be conducted and variables significantly associated with self-referral will be entered into the model. Since the study sample size will only allow for having 3 variables in the

model, more than one regression model may be necessary. If this is the case, a Bonferroni adjustment will be used to account for multiple comparisons.

*Secondary analysis:*

Quality of life scores will be compared within and between groups. For the within group comparison a two-sided dependent t-test will be conducted using the pre-study and 3-month quality of life scores for each group. To determine if a change in quality of life (difference between pre-study and 3-month quality of life scores) is statistically significant and mixed between-within subjects analysis of variance will be conducted.

All participants will complete a Urinary Symptoms questionnaire (ICIQ-FLUTS) which consists of ordinal categorical responses to questions related to urinary symptoms. Each question has five response options. For each question, each response category will be assigned a numeric value depending on the severity of the symptom (1= no symptoms; 5=severe symptoms). For each participant, improvement in symptoms will be determined by a reduction in the ordinal value. Improvement in UI symptoms will be compared between groups using a chi-square test.

Investigators are also interested in knowing if self-screening results in a higher proportion of participants initiating medication of UI during the study period. Therefore, the proportion of participants in each group who started medication for UI during the study period will be compared using a chi-square test.

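### Both arms can sit within one seniors' centre, and the plan's remark on overlap between centres does not protect the control arm from exposure to the intervention

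*Combined protocol and SAP*

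**What the plan says.** The design rests on a clean contrast. Under Study Design, the intervention group self-screens and "the control will not be exposed to self-screening". The Intervention paragraph adds a fact sheet, contact details for the local clinic and a website link.

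The only reassurance about mixing is under Setting: the centres serve large and different groups of seniors, "so overlap in membership is not expected to be an issue". Under Sampling and Recruitment, people are invited through the centres' e-mail lists and allocated one at a time: after consent, "the Research Assistant (RA) will choose the next available envelope to reveal which arm the study participant will be assigned". No stratification or clustering by centre or household is described.

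Two other steps involve exposed people from the same centres. Before the trial, "the self-screening tool will be pre-tested with 5 older adults attending participating seniors centres/organizations". Afterwards, self-screened participants are offered focus groups: "At the end of 3-months from study entry, in conjunction with survey completion, participants will be invited to participate in a focus group". The Limitations section recognises one source of bias toward the null, namely that eligibility screening may itself prompt controls to act.

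**The concern.** Separate membership between centres protects the contrast only when the centre is the unit of allocation. With individual allocation, a control and a self-screened participant can attend the same centre, and the overlap sentence does not bear on that.

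Three features of the plan leave a way for exposure to reach controls:

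- **Pre-test users.** Nothing in the eligibility criteria bars them from enrolling later. One who enrolled and drew control would already have used the tool.
- **Portable materials.** A form, a fact sheet, clinic details and a link are easy to pass on, and the visible text makes no request not to share them.
- **Focus-group timing.** Invitations follow each person's own three-month point. If entry is staggered, self-screened members could be discussing self-referral while some controls are still in follow-up.

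Controls prompted in this way would act more often. The difference would shrink, and a null result would be harder to read as evidence about the tool.

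**Working it through.** **Inputs from the documents (Sampling and Recruitment; Primary analysis).** Control rate: "there was a 14% self-referral rate without an intervention". Effect: "we hypothesize a 61% incremental increase in self-referral in the arm receiving the intervention". Power 80%, p < .05, 12 per arm. Test: "A chi-square test will be conducted to determine if the self-screening process is associated with self-referral to a health professional". Sidedness is not stated; two-sided is assumed.

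**Step 1: the plan's own sample size.** Read as 61 percentage points, the rates are 0.14 and 0.14 + 0.61 = 0.75, with mean 0.445. The pooled-variance formula gives

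n = [1.96·√(2 × 0.445 × 0.555) + 0.842·√(0.14 × 0.86 + 0.75 × 0.25)]² / 0.61² = (1.378 + 0.467)² / 0.372 ≈ 9.1, so 10 per arm.

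With continuity correction it is 13 per arm. The plan's 12 lies between the two, and exact Fisher power at 12 per arm is 83%, so the figure reproduces. Other readings do not fit: 14% against 61% needs 16 to 20 per arm, and a relative increase (0.14 × 1.61 = 22.5%) needs 321 to 344.

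**Step 2: dilution.** Let c be the share of controls exposed; the documents give no value. As an upper-end assumption, let exposed controls act at the full intervention rate. Then

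control rate = 0.14 + 0.61c; difference = 0.61(1 − c).

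Power is found by enumerating all 12-against-12 tables and summing the binomial probabilities of those rejected at 0.05, for the uncorrected chi-square and the two-sided Fisher test.

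| Controls exposed | Control rate | Difference (points) | Chi-square power | Fisher power |
|---|---|---|---|---|
| 0% | 14% | 61.0 | 92% | 83% |
| 10% | 20% | 54.9 | 85% | 71% |
| 20% | 26% | 48.8 | 74% | 58% |
| 30% | 32% | 42.7 | 62% | 45% |

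**Step 3: a weaker effect of exposure.** If exposure carries half the effect (also an assumption), control rate = 0.14 + 0.305c. Exposure of 10, 20 and 30% then gives control rates of 17, 20 and 23%, and chi-square power of 89, 85 and 80%.

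**Step 4: dependence on numbers followed up.** If all 36 recruits are evaluable (18 per arm), 20% exposure under the step 2 model leaves chi-square power of 89% (Fisher 81%). If half are lost (9 per arm), power is 80% (Fisher 66%) with no exposure and 55% (Fisher 41%) at 20%.

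**The case against.** The strongest reply is that every route is speculative or small.

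- **Pre-test users.** A reader might infer that all five would qualify for the trial. The documents do not support that: the Pre-test paragraph says only that they are older adults attending the centres, and is silent on symptoms, prior referral and the other criteria. It also does not say that they receive the fact sheet or link. What stands is that no rule excludes them. Nor would the chance of one of them drawing control measure the bias; the share of controls exposed does that.
- **Social contact.** Thirty-six people come from several organisations of more than 300 seniors each, and the Background describes stigma and silence around the condition. This may well keep exposure low. It does not undo exposure that a pre-test user already has.
- **Households.** Couples in opposite arms are not mentioned anywhere; the route is inferred from the absence of a rule.
- **Focus groups.** Attendees have already had the intervention, and groups of 10 to 12 cannot fill until much of that arm has finished. The route needs staggered entry, which is not stated, although allocation one envelope at a time is compatible with it.
- **Detection.** A reader might infer that nothing planned would reveal exposure. That cannot be verified: the three-month questionnaire and the invitation letter are cited but not included, and either could contain an exposure question or a request not to share.
- **Size.** Full transfer of effect is close to a worst case, because the intervention is completed screening plus information. The planned test is a chi-square, and by that test 10% exposure still leaves 85% power.

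The trial is also a pilot and the bias is conservative. These points limit the size and certainty of the problem. They do not make the overlap sentence relevant to individual allocation.

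**Conclusion.** The point holds as a cheap improvement, not as a demonstrated flaw in the comparison. The plan as written permits some control exposure within centres, and its one reassurance addresses a different question. The direction, toward no difference, is clear; the amount is unknown.

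Under full transfer at 12 per arm, chi-square power stays above the 80% target at 10% exposure and falls below it at 20% (74%). Under half transfer it is still about 80% at 30% exposure. These figures rest on 14% against 75%, a two-sided 0.05 test and assumed exposure rates. They do not predict what will happen in this trial. A reader might go further and conclude that a null result would be uninterpretable; the documents do not support that, because they establish neither how many controls would be exposed nor how strongly they would respond.

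**What to change.** 1. **Sampling and Recruitment:** add participation in the pre-test of the tool to the exclusions.
2. **Intervention:** ask intervention participants not to share the tool or fact sheet until follow-up ends.
3. **Post-Intervention Focus Groups:** hold the groups only after the last participant's three-month call.
4. **Procedures (three-month call):** after the action questions and before the symptom questions, ask controls whether, before this call, they had seen another participant's screening form, fact sheet or website link. Report that proportion beside the primary result. The order matters because the call's symptom items cite the same instruments (references 18 and 19) as the screening tool; asked later, the answer about the form could not be interpreted.
5. **Limitations:** add within-centre contamination.

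A one-per-household rule is optional, since that route is only inferred. None of this changes the randomisation or the primary test. The cost is a small amendment, up to five volunteers lost to recruitment, later focus groups and one extra call item.

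### Recruiting 36 does not allow for 50% drop-out: about 18 would complete, not the 24 the plan requires; 36 covers only 33% drop-out

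*Combined protocol and SAP*

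**What the plan says.** The sample size argument is in the Sampling and Recruitment paragraph of the Methods.

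- **Control rate:** from other work, "there was a 14% self-referral rate without an intervention".
- **Effect:** "we hypothesize a 61% incremental increase in self-referral in the arm receiving the intervention".
- **Required number:** for 80% power at the 0.05 level, the sample size "is 24 participants (12 older adults per arm").
- **Drop-out allowance:** "In factoring the potential for a drop-out rate of 50%, a sample size of 36 participants will be recruited".
- **Allocation:** "Excel randomization function will be used to assign participants to one of the two arms". Sealed envelopes are described, but no blocking or fixed number per arm.

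Under Data Analysis, Primary analysis, the test is named: "A chi-square test will be conducted to determine if the self-screening process is associated with self-referral to a health professional". The plan does not say whether it is continuity-corrected.

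The outcome is collected once, as described under Data Collection: "Three months following study entry participants from both groups will receive a phone follow-up". The documents contain no rule for replacing participants who drop out and none for imputing a missing primary outcome.

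**The concern.** A drop-out rate is a share of those recruited. Half of 36 is 18, so the recruitment target does not deliver the 24 the plan says it needs. Because the primary outcome comes from the three-month call, a participant lost before then contributes nothing to the primary comparison.

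The study is called a pilot, but the Methods say it will test effectiveness, and it has a power target and a hypothesis test. The recruitment number is therefore part of the design. If the sentence stands, the team will believe the trial can lose half its participants and keep its stated power. It would in fact be below its own requirement once drop-out passes one third.

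There is also a knock-on effect. The focus groups are to draw 10 to 12 participants from the self-screening arm at three months. With about 9 completers in that arm, even 10 in total could not be reached.

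**Working it through.** **Inputs.** Required completers 24 (12 per arm), drop-out 50%, recruits 36, control rate 14%, increase 61%, power 80%, level 0.05 (all Sampling and Recruitment); chi-square test (Primary analysis). Two-sided testing is my assumption, since the plan does not state sidedness.

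**1. Where the 24 comes from.** Read the effect as 14% versus 14 + 61 = 75%. The pooled two-proportion formula is

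n per arm = [1.960·√(2·p̄·(1−p̄)) + 0.842·√(p₁(1−p₁) + p₂(1−p₂))]² / (p₂−p₁)²

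With p̄ = 0.445, this is [1.960·√0.494 + 0.842·√0.308]² / 0.61² = 9.1, rounded up to 10 per arm, or 20 in total. With continuity correction it is 13 per arm, or 26. The plan's 24 lies between the two, and exact power at 12 per arm is 83% with Fisher's test or the corrected chi-square. So 24 is a plausible base on this reading.

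**2. Where the 36 comes from.** 24 × (1 + 0.5) = 36. This adds 50% of the required number instead of dividing by the share retained.

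**3. Correct inflation.** 24 / (1 − 0.5) = 48, or 24 per arm.

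**4. What 36 delivers.**
- Completers at 50% drop-out: 36 × 0.5 = 18, about 9 per arm. Shortfall: (24 − 18) / 24 = 25%.
- Drop-out that 36 can absorb: 1 − 24/36 = 33.3%.
- If each participant drops out independently with probability 0.5, P(at least 24 of 36 complete) = 0.033.

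**5. Effect on power.** Exact binomial enumeration, two-sided 0.05, equal arms:

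| Assumed rates | Test | 12 per arm | 9 per arm |
|---|---|---|---|
| 14% vs 75% | Chi-square, uncorrected | 92% | 80% |
| | Fisher's exact | 83% | 66% |
| | Chi-square, corrected | 83% | 55% |
| 14% vs 61% | Chi-square, uncorrected | 72% | 59% |
| | Fisher's exact | 55% | 41% |
| | Chi-square, corrected | 55% | 31% |

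If the 61% is a relative increase (14% × 1.61 = 22.5%), power is at most 6% at either size.

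**6. Unequal arms.** Eighteen completers need not split 9:9. For 14% versus 75% and splits from 6:12 to 12:6, power is 77–82% uncorrected, 66–78% with Fisher's test, and 52–64% corrected.

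**The case against.** The strongest reply is that the error may cost little. The plan names a chi-square test and mentions no correction. With the uncorrected test and 14% versus 75%, 18 completers still give 79.6% power, essentially the target. For that test the 24 was generous: it gives 92%, and the formula asks for only 20. Repairing the sentence without adding participants also leaves recruitment, allocation and analysis as they are, which suggests a minor point.

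The calculation is right, and it should be stated openly. It does not rescue the sentence. The plan neither rules out a correction nor says which two proportions the 61% refers to, so 80% is one favourable combination and not something the plan claims. The plan attaches 80% power to 24 completers, and the statement that 36 protects that number at 50% drop-out is false whatever the test.

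Two narrower objections stand:
- The low power for 14% versus 61%, and for the relative reading, is mostly not caused by drop-out. It is already below 80% at 24 completers because the effect is loosely worded. Drop-out accounts only for the further fall, for example from 72% to 59% uncorrected.
- The 66% and 55% figures hold for a 9:9 split and should be labelled so or given as ranges.

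The only reading that makes 36 correct takes the 50% as a top-up on 24, which is not what a drop-out rate means.

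**Conclusion.** The concern holds, and the sentence must be corrected. At the plan's own drop-out rate, 36 recruits give about 18 completers against 24 required. The number 36 matches a drop-out rate of 33%, and a drop-out rate of 50% needs 48. These figures follow from the plan's own numbers and rest only on the ordinary meaning of a drop-out rate and on drop-outs having no primary outcome.

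The loss of power is conditional. At 14% versus 75%, two-sided 0.05 and nine per arm, power ranges from about 80% with the uncorrected chi-square test down to 55% with the corrected one. It also depends on how the 18 divide between arms.

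**What to change.** Keep 36 and replace the drop-out sentence with wording such as:

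> Recruiting 36 participants allows for a drop-out rate of 33% (24 completers). At 50% drop-out about 18 would complete. Assuming 14% versus 75% self-referral, a two-sided 0.05 level and nine completers per arm, power would be about 80% with the uncorrected chi-square test, 66% with Fisher's exact test, and 55% with continuity correction.

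So that the power statement can be read, say which two proportions the 61% increase means and whether the chi-square test is corrected. If 14% versus 61% is meant, the three figures at 18 completers become 59%, 41% and 31%.

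This costs wording only: a less favourable stated tolerance (33% instead of 50%) and no extra participants. If the 50% allowance is to be kept as a requirement, recruit 48, which is 48 − 36 = 12 more.
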